#### 8.4.1 Specific criteria for withdrawal (if applicable)

#### 8.5 Replacement of individual subjects after withdrawal

If a subject is withdrawn from the study within two weeks from inclusion, the subject will be replaced. After this time period, subjects will not be replaced.

# 8.6 Follow-up of subjects withdrawn from treatment

Not applicable.

# 8.7 Premature termination of the study

Not applicable.

#### 9 SAFETY REPORTING

#### 9.1 Temporary halt for reasons of subject safety

Not applicable

# 9.2 AEs, SAEs and SUSARs

Our wearable sensor (NightWatch) has been developed in cooperation with Livassured and a group of researchers, the Dutch Teleconsortium. After production of a prototype, different usability tests have been performed to examine the product. Special attention has been paid to patient safety.

NightWatch is CE certified as a Medical Device Class I.

# 9.2.1 Adverse device events (ADEs)

Adverse device events (ADEs) are defined as any undesirable experience occurring to a subject during the study, causally related to the study device. All adverse device events reported spontaneously by the subject or observed by the investigator or his staff will be recorded.

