# 9.2.2 Serious adverse events (SAEs)

A serious adverse (device) event (SA(D)E) is a serious (leading to hospitalization or (near)-death) unfavorable and unintended sign (including an abnormal finding), symptom, or disease temporally associated with the clinical trial whether or not related to a failure of the device to alarm. A SAE will be reported within 7 days to the METC . All subjective or presumed complaints will be reported. We do not expect serious adverse events causally related to NightWatch (SADE). Previous trials (LICSENSE Phase I-III) have indicated that the NightWatch is tolerated well with respect to comfort and skin reactions.

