# 9.4 Follow-up of adverse events

All AEs will be followed until they have abated, or until a stable situation has been reached. Depending on the event, follow up may require additional tests or medical procedures as indicated, and/or referral to the general physician or a medical specialist.

9.5 [Data Safety Monitoring Board (DSMB) / Safety Committee] Not applicable.

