If a high frequency of false alarms causes a big burden on parent(s)/guardian(s), they can contact the researcher to discuss this problem. The researcher can then offer them the possibility to switch off the audible alarms. Because the annotation process takes some time, we are not able to give feedback on the reason for these false alarms, and if they are really false alarms, at that time. When the analyzation process is completed, the researchers will give the parent(s)/guardian(s) the opportunity to look at the recordings of their child to learn more about their seizures and reasons for false alarms.

At the end of the study, we will share the performance data of NightWatch with the subject's neurologist. He/she will invite the subject and/or his/her parent(s)/guardian(s) to discuss this performance and user experiences. As an objective third party, the neurologist can then advise them to keep NightWatch for further use or might advise to use another seizure detection device.

According to the performance of NightWatch, we will offer the following options at the end of the study:

In case of good performance, combined with satisfying use, NightWatch can give the family a benefit. In these cases, we would like to offer them the possibility to keep NightWatch for further use. We believe that offering NightWatch for free or a small amount of money can give an undesirable financial incentive to participate. It should be noted that currently none of the seizure detection devices are reimbursed. The most frequently sold seizure detection device (bed sensor) that was shown to have a poorer performance in our previous trial (LICSENSE NTR4115) has a higher cost price (€1700,-) compared to the NightWatch (€1500,-). For the above reasons, we found a 50% reduced rate of €750,- to be reasonable, since this is equal to the production costs. Besides, Livassured will offer a two year guarantee for the service and support of the device.

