#### 12 STRUCTURED RISK ANALYSIS

#### 12.1 Potential issues of concern

# 12.2 Synthesis

Implementation of our wearable sensor device (NightWatch) is not considered to pose any substantial risk. Since the efficacy of NightWatch has not yet been proven in children in a family home setting, we cannot guarantee that subjects and parents/guardians can rely completely on this device. There is a chance that parent(s)/guardian(s) will become less alert during the study. To minimize this risk, we will give them extensive information that especially emphasizes this matter.

Study participation can be a burden for the family, due to the impact of the devices on their privacy, the impact of false alarms and the time spend on completing questionnaires, interviews and a diary. It does, however, also give the families better insight in seizure behavior of their child and shows them the possible utility of seizure detection.

If the NightWatch becomes uncomfortable or causes any distress, the wearable device will be removed and the subject will be withdrawn from the study. In case of alarm fatigue, the parents/guardians can stop the NightWatch measurements and contact the researcher to switch off the alarms. If the subject or parents/guardians wish(es) to stop the video registration for any reason, they can contact the researchers to switch off the video recordings or even all recordings.

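### Non-serious events are recorded only if caused by the device, so the plan does not ensure capture of non-hospitalized injuries after a seizure without an alarm

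*Combined protocol and SAP*

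**What the plan says.** Section 9.2.1 defines an adverse device event as "any undesirable experience occurring to a subject during the study, causally related to the study device". Its recording rule covers that class and relies on passive reporting: "All adverse device events reported spontaneously by the subject or observed by the investigator or his staff will be recorded".

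Section 9.2.2 treats serious events differently. They count when "temporally associated with the clinical trial whether or not related to a failure of the device to alarm", but the threshold is "leading to hospitalization or (near)-death". The same section adds a short sentence that subjective or presumed complaints are reported too. It does not say to whom, or whether non-serious events are meant.

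Section 9.4 states: "All AEs will be followed until they have abated, or until a stable situation has been reached". Section 9 does not define AE. The table of contents lists 9.2.1 as adverse events, while the heading in the body reads adverse device events.

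On risk, Section 12.2 says that complete reliance on the device cannot be guaranteed, and adds: "There is a chance that parent(s)/guardian(s) will become less alert during the study". Section 1 lists injuries among the consequences of seizures in general.

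Parents are invited to keep a seizure diary in both periods (Section 3). The parent who responds to an alarm also logs events (Section 8.3). Neither diary is linked to Section 9, and Section 10 contains no analysis of adverse events.

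**The concern.** An alarm device can harm a child indirectly: the family relies on it, the alarm does not come, and a seizure goes unattended. An injury of that kind is hard to attribute when it happens. A rule that asks for attribution before recording puts the filter at the wrong step, because the relation to the device is something to work out from recorded events.

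Three things are at stake. A report of few device-related events could not be told apart from events that were never entered. Two sites could treat the same injury differently, because nobody is named to judge causality. And no baseline event can meet the definition in 9.2.1, since NightWatch is not in use then, so the before-and-after design yields no comparable count for the months without the device.

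**Working it through.** No figure in the plan underlies this point, so the main check sets the rules side by side. The cases are illustrative.

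| Event | Section 9.2.1 | Section 9.2.2 | Recorded? |
|---|---|---|---|
| Skin reaction under the bracelet | Device-related | Not serious | Yes, if reported or observed |
| Injury after a seizure without an alarm, child admitted | Not needed | Serious, causality not required | Yes |
| Same injury, no admission and not near-fatal | Only if judged caused by the device | Below threshold | Depends on a judgement assigned to no one |
| Same injury in the baseline months | Cannot qualify: no device in use | Below threshold | No explicit rule |

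The third and fourth rows are the gap.

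**Would such an event surface in another way?** Section 3 plans routine screening of 5% of the nocturnal video without alarms, rising to 10% if the check after 20 subjects requires it. Most alarm-free recordings would not be reviewed, so staff observation cannot be relied on for missed seizures. Section 9.2.1 names the subject, aged 4 to 16 (Section 4.2), as the spontaneous reporter and does not mention the parents.

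**Scale of missed alarms.** Inputs from Section 4.4: 60 children, about 540 seizures at the minimum of one per week over two months, target sensitivity 80%, drop-out allowance about 30% (stated there for the feasibility study).

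- Plan's seizure count: 540 / 60 = 9 per child, that is, one a week for about nine weeks. The figure reproduces.
- Seizures without an alarm at target: 540 × (1 − 0.80) = 108.
- If drop-out also removed 30% of the seizures (an assumption): 540 × 0.70 = 378, and 378 × 0.20 = 75.6, about 76.

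**Observation time for a descriptive rate.** 60 × 2 = 120 child-months per period if all children complete. If 30% contributed no time (an assumption), 42 × 2 = 84.

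The 108 shows only that seizures without an alarm are expected in this trial. It does not count harms. It also says nothing about excess harm from reliance, because at baseline no seizure triggers a NightWatch alarm.

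**The case against.** The case on the other side has real substance.

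- **A reader might infer that these injuries are excluded.** The documents do not support that. Section 9.2.1 does not place a failure to alarm outside device causality, and the phrase "whether or not related to a failure of the device to alarm" in 9.2.2 shows that the authors had this pathway in mind. Such an injury could be judged an adverse device event. What stands is that the plan does not say so.
- **The sentence on complaints in 9.2.2 carries no causality condition.** This is true, and it may have been meant as a catch-all. Its place under serious events and its unstated scope keep it from being a dependable rule for non-serious injuries.
- **A reader might infer that the events are never collected.** This is too strong. The diary, the medical consumption questions about the child at T0 and T2, the T2 survey and interview items on negative effects, and the video could all hold them. None is tied to safety recording.
- **A reader might call 9.4 a contradiction of 9.2.1.** If AE there means ADE plus SAE, nothing conflicts. It is an undefined term that reads wider than what is recorded.
- **A reader might cite "Because the annotation process takes some time" in Section 11.4 as proof that causality cannot be judged in time.** That sentence concerns feedback to parents on false alarms. A parent who finds an injured child may well know whether an alarm sounded, and 9.2.1 sets no deadline for the judgement.
- **No single sentence names injury after a missed seizure.** Section 9.2.2 names failure to alarm, Section 12.2 reduced alertness, and Section 1 injuries. Joining them is an inference, though a short one.
- **Comparing safety between periods is not an objective in Section 2.** This stands, and limits any comparison to description.

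**Conclusion.** The point holds as a gap in what the plan ensures. For non-serious events the only explicit recording rule depends on device causality, while the rule for serious events does not. A non-hospitalized injury after a seizure without an alarm therefore enters the safety data only after a judgement for which the plan gives neither a criterion nor a responsible person. This is a stated rule that yields weaker safety data, so it goes beyond missing detail.

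Its size cannot be given in injuries, because the documents contain no injury rate. The only scale available is about 108 seizures without an alarm at the plan's targets, or about 76 under the drop-out assumption. Both figures rest on one seizure per week and 80% sensitivity being realised. The primary accuracy endpoints are unaffected. What is affected is how far a statement of few or no device-related harms could be trusted.

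**What to change.** - In 9.2.1, record every night-time or seizure-related injury of the child, whatever the presumed cause.
- Collect it with the same fixed line in the seizure diary in both two-month periods. Do not add a prompt in one period only: a question at the disk-change visits, which take place only during exposure, would find more events there and bias the comparison.
- For exposure nights, classify the relation to the device afterwards (alarm, no alarm, no valid signal) from the NightWatch log and any video the family has not had deleted, looking up the night in question. This must not be a condition for recording. Name who classifies, and state whether harm after a failure to alarm counts as device-related.
- Report counts per child-month for both periods, descriptively.
- Define AE, ADE and SAE once and use them consistently in 9.2.1, 9.2.2 and 9.4. State the scope of the sentence on complaints.

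The cost is one diary line, a look-up for each reported exposure night, and a small table. Some events unrelated to the device will be logged, and few events are expected. Diary completeness limits the comparison, since parents are only invited to keep the diary. Baseline and daytime events cannot be classified from nocturnal logs or video.

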#### Intervention

After two months, the researcher will visit the home to install the equipment. A camera and microphone will be placed on a pole, secured between floor and ceiling, next to the subject's bed. A suitcase containing a MacBook laptop and an external hard drive for data storage will be placed in the subject's room. The subject will be instructed to wear the NightWatch bracelet every night around the upper arm. When NightWatch is removed from its docking station, it will start running automatically. All recorded data (NightWatch, video and audio) will be stored automatically to the

MacBook and copied on hard drive. The researchers will replace the hard-drive every 2 weeks and store all recordings safely at SEIN or Kempenhaeghe for analysis. During the first weeks, the hard drive will be switched more often, in order to detect systematic errors in time.

In the morning, NightWatch must be connected to the docking station, when this happens, recordings stop automatically. During the study, subjects (or parent(s)/guardian(s)) do not have to switch any on/off button for the recordings. When NightWatch detects a seizure, it generates an alarm to the alarm station part of the NightWatch system at the parent(s)/guardian(s) bedroom. When the alarm goes off, the responding parent/guardian will check on their child and act upon the situation. He/she will keep a diary of all events. The SDD intervention period will last two months.

In case of technical problems, parent(s)/guardian(s) can contact the technical trial coordinator. If the parent(s)/guardian(s) give their consent, the coordinating investigator will be able to look into the study Macbook at their home from a distance true a secured program to solve technical problems. If the problem is not solved, the technical trial coordinator will visit the participant's home.

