# 8.4 Withdrawal of individual subjects

Subjects can terminate the study at any time for any reason if they wish to do so without any consequences. The investigator can decide to withdraw a subject from the study for urgent medical reasons or important unforeseen events (e.g. material deficiencies). If the subject shows any signs of resistance to wear the device, the investigators are obliged to withdraw the subject from the study.

Researchers will ask for the reason of withdrawal, because this can give them information about the feasibility. Subjects and their parent(s)/representative(s) are not obliged to answer this question.

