#### 11.3 Objection by minors or incapacitated subjects (if applicable)

We will make sure that a minor or incapacitated subject will never be forced to participate in our trial. Subjects aged 12-16 must give a co-consent in addition to the informed consent of their parent(s)/representative(s). The subject can only participate if both parties have given consent. Younger subjects (age 4-12) will be informed about the study in the best way we can (by means of a specific information letter, adjusted by age). If a minor or incapacitated subject gives any objection against participation, the subject will not be included in the study. Next to that, all subjects will be able to stop participating in the study, at any moment during the study. When the subject is able to communicate this (non)verbally, the wish of the subject will be honored. If the NightWatch is experienced as a nuisance, or makes the subject uncomfortable, the device will be removed in consultation with the parent(s)/representative(s).

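### The adverse device event record relies on spontaneous reports by the child or on staff observation, with no scheduled question to parents, so skin and comfort problems may be under-counted in it

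*Combined protocol and SAP*

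**What the plan says.** Section 9.2.1 defines an ADE broadly, as "any undesirable experience occurring to a subject during the study, causally related to the study device", so discomfort and skin reactions fall within it. The same section then says how events enter the record: "All adverse device events reported spontaneously by the subject or observed by the investigator or his staff will be recorded". Parents and guardians are not mentioned there, and no question, checklist or skin check is scheduled.

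Section 9.2.2, under serious events, adds "All subjective or presumed complaints will be reported" and gives the basis for expecting few problems: "Previous trials (LICSENSE Phase I-III) have indicated that the NightWatch is tolerated well with respect to comfort and skin reactions".

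Discomfort also has consequences for participation. Section 8.4 states: "If the subject shows any signs of resistance to wear the device, the investigators are obliged to withdraw the subject from the study". Section 12.2 states: "If the NightWatch becomes uncomfortable or causes any distress, the wearable device will be removed and the subject will be withdrawn from the study". Section 11.3 differs: the device comes off after discussion with the parents or representatives, and withdrawal is not mentioned.

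Staff are regularly in the home. Under section 8.3 (Intervention), "The researchers will replace the hard-drive every 2 weeks", and section 11.4 describes a trial nurse visiting every one to two weeks. These visits are described for exchanging the disk and deleting footage.

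**The concern.** The rule is passive, and it names reporters who are poorly placed to report. Inclusion starts at age 4, and the consent sections allow for children who cannot consent themselves. The armband is worn at night, when no staff are in the house. The parent, who is the adult on the spot, is not a named reporter.

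The protocol itself identifies comfort and skin reactions as the relevant tolerability outcomes, and section 12.2 acknowledges that efficacy in children in a family home has not yet been proven. A short ADE list from this trial could be read as evidence that children tolerate the armband at home. If nobody was asked at set times, a short list partly reflects not asking, and the reader cannot separate the two explanations.

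**Working it through.** The documents give no expected ADE rate, no safety sample size and no ADE analysis, so there is no stated figure to reproduce. The check has two parts.

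**1. Does another route feed the ADE record?**

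- *Complaints sentence (9.2.2).* It states that complaints are reported but gives no method of eliciting them.
- *Reason for withdrawal (8.4).* It is asked in order to learn about feasibility, and answering is optional. No link to the ADE record is stated.
- *Survey T2 (8.1.2, Table 1).* It asks parents about positive and negative effects, once, after the device period. No skin item is named, and no rule covers children who stopped early. Table 3 summarises survey answers by median, mode, range and extremes, which does not count affected children.
- *Interviews (8.3).* Only a subgroup is interviewed.
- *CSI, PSQI, EQ-5D-5L (Tables 1 and 2).* These cover strain, parental sleep and quality of life, not skin or comfort under the armband.
- *Video review (section 3).* Nurses check alarms and marks, plus 5% of recordings without alarms. Visible distress might be seen, but not the skin under the band.
- *Follow-up.* Section 9.4 follows all adverse events until they abate or stabilise, while section 8.6 marks follow-up of withdrawn subjects as not applicable.
- *Analysis (section 10).* No summary of ADEs is planned.

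Several routes may bring a problem to light, but none is stated to end in the ADE record.

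**2. How much could incomplete capture matter?**

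Inputs: n = 60 children (section 4.4), taken as all reaching the device period. The true share of children affected (p) and the share of affected children who get recorded (c) are assumptions.

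*Upper bound when no event is recorded.* The one-sided 95% bound on the recorded risk is 1 − 0.05^(1/60) = 4.87%. The recorded risk is p × c, so the bound on p is 4.87% / c:

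| Capture c (assumed) | Upper bound on p |
|---|---|
| 100% | 4.9% |
| 75% | 6.5% |
| 50% | 9.7% |
| 25% | 19.5% |

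*Chance of an empty record.* This is (1 − p × c)^60. With p = 10% assumed:

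- c = 100%: 0.90^60 = 0.2%, with 60 × 0.10 = 6.0 affected children expected in the record.
- c = 50%: 0.95^60 = 4.6%, with 3.0 expected.
- c = 25%: 0.975^60 = 21.9%, with 1.5 expected.

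**The case against.** The best defence is that comfort problems have several other ways of surfacing. Parents receive survey T2 and are asked about negative effects. Families who leave are asked why. Section 9.2.2 says complaints are reported. Nurses review part of the video, and hours of use are a study parameter. The acceptability evidence comes mainly from surveys and interviews; the ADE count is neither a primary nor a secondary parameter, and the device is CE Class I with good earlier tolerability stated. All of this stands. It rules out the reading that section 9.2.1 is the only way a problem could become known. It does not show that the ADE record is complete, because no link to that record is specified.

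A reader might also infer that families will keep quiet about discomfort in order to stay in the trial. No passage shows this. Withdrawal can equally expose an event, since staff learn of it and ask for the reason.

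The capture fractions in the illustration are not from the documents, and zero events is a hypothetical. That is fair, and the figures should be read only as showing sensitivity. Shrinking the denominator by the 30% drop-out allowance of section 4.4 would be wrong: that allowance is stated for the feasibility study, and a child who stops after wearing the device still belongs in the safety denominator.

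**Conclusion.** The point holds for the ADE record. The stated method is passive, leaves out parents, schedules no question on skin or comfort, and has no link from withdrawal reasons or T2 answers. Skin and comfort problems may therefore be under-counted there. The stronger statement that they will be under-counted is not supported, because the documents give neither an event rate nor a capture fraction.

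The size is unknown. Under the assumptions above, halving capture doubles what a clean record can exclude, from 4.9% to about 9.7%; at 25% capture it is 19.5%. If some children leave during the two-month run-in and never wear the device, the denominator falls below 60 and every bound widens.

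The diagnostic performance endpoints do not depend on this point. It is worth correcting before the device period because questions not asked at the time cannot be fully recovered later.

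**What to change.** - **Section 9.2.1.** Record all ADEs reported by the subject or the parent/guardian, or observed by the investigator or staff.
- **Section 8.3.** At each hard-drive visit, at T2 and at withdrawal, ask the parent, and the child where able, a short fixed set of questions on skin under the armband and on comfort. Answering stays optional.
- **Link.** Enter device-related answers, including those given as withdrawal reasons or in survey T2, as ADEs.
- **Section 10.** Report the number of children with at least one ADE among all who wore the device, with an exact confidence interval, and events per night worn.
- **Reconcile.** Sections 8.4, 11.3 and 12.2 differ on what follows discomfort, and sections 8.6 and 9.4 on follow-up. The sponsor should settle both; this review does not choose the rule.

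The cost is a few questions at contacts that mostly exist already. Section 4.4 implies about nine weeks of monitoring (540 seizures / 60 children at one per week), so fortnightly exchange gives 9 / 2 = 4.5, or about four to five visits per child. There are two downsides. More minor events will be recorded than under passive reporting. Asking about comfort may also bring more discomfort to light and, under sections 8.4 and 12.2 as written, more withdrawals, which would draw on the 30% drop-out allowance.
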